8. DEMOGRAPHICS AND BASELINE CHARACTERISTICS

Demographics and baseline characteristics, prior/concomitant medications and procedures will be reported separately for Phase 1b and Phase 2. Demographic and baseline disease characteristics will be summarized by dose cohort for FAP (Phase 1b) and by treatment arm and overall for the ITT, mITT and Safety populations (Phase 2). In addition, for Phase 2, the Pearson Chi-square test (for categorical parameters with more than 2 categories), Fisher exact test (for binary parameters and parameters which have more than 20% of cells with expected frequencies less than 5) and the Wilcoxon sum rank test (for continuous parameters) will be provided as descriptive purpose. Due to the limited sample size and multiplicity, it may not be suitable to use those p-values to assess the comparability of two randomized treatment arms in each setting for demographic, baseline disease characteristics, and AML diagnosis history.

Individual subject listings will be provided to support the summary tables.

8.1. Demographics

Age (year), height (cm), weight (kg), body mass index (kg/m^2), body surface area (m^2), and other continuous baseline characteristics will be summarized using descriptive statistics (N, mean, standard deviation, Q1, Q3, median, minimum, maximum), while age group (<65 years, ≥ 65 -<75 years, ≥ 75 years), gender, ethnicity, race, geographic region and other categorical variables will be provided using frequency tabulations (count, percent) by dose cohort groups (Phase 1b) and by treatment arm and overall (Phase 2).

Age or year of birth will be recorded on eCRF. Where age is not recorded, age will be calculated as follows: Age = year of informed consent – year of birth.

Body mass index (BMI) will be calculated as follows: $\text{BMI} (\text{kg}/\text{m}^2) = \text{weight in kg} / (\text{height in m})^2$.

If not collected in eCRF, body surface area (BSA) will be calculated as follows: $\text{BSA} (\text{m}^2) = \text{weight} (\text{kg})^{0.425} \times \text{height} (\text{cm})^{0.725} / 139.2$.

8.2. Baseline Disease Characteristics and AML Diagnosis History

The number and percentage of subjects in each of the following categories will be summarized by dose cohort (Phase 1b) and treatment arm (Phase 2) and overall (Phase 1b and Phase 2 separately). Continuous variable will be summarized by mean, standard deviation, median, Q1, Q3, minimum, and maximum.

8.2.1. Baseline Disease Characteristics

Baseline value is defined as the last non-missing data on or before the first dose of the study drug, unless otherwise specified. Baseline values from the parameters below, but not limited to, will be tabulated:

1. IDH mutation type: IDH1 or IDH2, and the sub-type (R172, R140, both R172 and R140) for IDH2 gene mutated subjects;
2. Eastern Cooperative Oncology Group (ECOG) performance status;

3. Eligibility for preselected to receive intensive chemotherapy;
4. Bone marrow blasts (%) as a continuous variable and a category variable (Category I: < 20%; 20% to < 30%; 30% to < 50%; ≥50%; Category II: <5%; 5% to < 25%; 25% to < 70%; ≥ 70%) from the screening BM aspirate sample;
5. Bone marrow blasts (%) from the screening BM biopsy sample (0-4%, 5-9%, 10-19%, ≥20%);
6. Blasts percentage from PB smear sample;
7. Cytogenetic Risk Status: better-risk, intermediate-risk, poor-risk, failure (local, central);
8. Baseline values of the following lab parameters: Hemoglobin (<80 g/L, ≥ 80 g/L), platelet count (< 50 x10⁹/L, 50 to <100 x10⁹/L; ≥ 100 x10⁹/L), absolute neutrophil count (ANC) (< 0.5 x10⁹/L, 0.5 to < 1 x10⁹/L, ≥ 1.0 x10⁹/L), white blood cells (WBC) (<15 x10⁹/L, 15 to < 30 x10⁹/L, ≥ 30 x10⁹/L), creatinine clearance (< 45 mL/min, 45 to < 60 mL/min, ≥ 60 mL/min); These parameters will also be summarized as continue variables;
9. Number of units of red blood cell (RBC), whole blood, platelet, plasma, and other (specify) transfusions;
10. Left ventricular ejection fraction (LVEF) by echocardiogram (ECHO) or multi-gated acquisition (MUGA) scan;
11. ECHO/MUGA findings (Normal, Abnormal and Unevaluable).

8.2.2. AML Diagnosis History

1. AML initial diagnosis: primary (i.e., de novo) or secondary (myelodysplastic syndrome (MDS) progression or myeloproliferative neoplasms (MPN), or therapy-related) according to WHO classification. If AML is secondary, number and percentage of subjects who has an antecedent hematologic disorder will be summarized, and type of the antecedent hematologic disorder will be tabulated too;
2. Time (months) from the initial diagnosis of AML, calculated from time of initial diagnosis to randomization date for phase 2 and the enrollment date for phase 1b.

8.2.3. Chromosomal Abnormalities at Baseline

The cytogenetics in each risk status (better-risk, Intermediate-risk, Poor-risk) at baseline will be summarized for Phase 2 only.

8.3. Medical History and Concomitant Disease

The medical and surgical history, as well as concomitant disease will be summarized by the Medical Dictionary for Regulatory Activities (MedDRA) Version 22.0 by system organ class (SOC) and preferred term (PT). Active concomitant disease will be summarized in separate tables.

8.4. Prior/Concomitant/Follow-up Medications/Procedures/Therapies

Prior medications/procedures are defined as medications/procedures/transfusions that were started prior to start of study drug or had a missing start date. If start date is missing and end date is before start of study drug will be considered as prior only.

Concomitant medications/procedures are defined as non-study medications/procedures/transfusions that are started on or after the start of study drug but before the end of the study treatment period or started before the start of the study drug and ended or remain ongoing during the study treatment period. The end of the study treatment period is defined as the earlier date of last dose of study drug + 28 days and the date of death.

Medications/procedures with missing start date but end date on or after start of the study drug and before the end of the study treatment period or with both missing start date and end date is also considered as concomitant medications/procedures/transfusions.

Follow-up medications/procedures are defined as non-study medications/procedures/transfusions that are started on or after the date of the end of the study treatment period.

All non-study medications and therapies will be coded by Anatomical Therapeutic Chemical (ATC) code and PT using the World Health Organization Drug Dictionary latest version. All procedures and surgeries will be coded by the Medical Dictionary for Regulatory Activities (MedDRA) Version 22.0 by system organ class (SOC) and preferred term (PT).

8.4.1. Prior/Concomitant/Follow-up Medications

All prior, concomitant and follow-up medications will be summarized in frequency tabulations (subject counts and percentages) and by World Health Organization ATC third level and PT. Listings will also be provided for general medications and concomitant QT prolonging medications.

Prior/concomitant/follow-up medications will be summarized and listed based on FAP for Phase 1b subjects, and ITT and Safety populations for Phase 2 subjects.

8.4.2. Prior/Concomitant/Follow up Procedures/Surgeries

The prior, and concomitant procedures/surgeries will be summarized in frequency tabulations (subject counts and percentages) by SOC and PT. Listings will also be provided.

Prior/concomitant/follow-up procedures/surgeries will be summarized and listed based on FAP for Phase 1b subjects, and ITT and Safety populations for Phase 2 subjects.

8.4.3. Prior/Subsequent Anti-cancer Therapies

This section includes both AML therapies and non-AML therapies. AML therapies include radiation, procedure/surgery, systemic and stem cell transplant. Non-AML therapies are for the other hematologic or non-hematologic malignancies.

While the eCRF form is called subsequent AML therapies, the form applies to Prior therapies (therapy started prior to the date of the first dose of study drug) and Subsequent therapies (Follow-up, cancer treatments that the subject started after the end of study drug) to treat the subject's cancer (disease under study and any other cancers).

Prior and subsequent therapies will be summarized separately in tables. All tables described in this section will be based on FAP for Phase 1b subjects, and ITT populations for Phase 2 subjects.

8.4.3.1. Prior/Subsequent Radiation Therapies

The number and percentage of subjects who had any prior/subsequent radiation therapy will be presented by dose cohort for the FAP (Phase 1b) and by treatment arm for the ITT population (Phase 2). Summaries will include number of subjects receiving any radiation therapy, as well as the frequency by type of radiation therapy received (i.e., external beam, radio-immuno therapy, brachytherapy, etc.), intent of therapy, and settings. For subjects received radiation therapy, treatment site, type of radiation therapy, location of external beam, start/stop date, dose, number of fractions, intent of therapy, and settings of therapy will be presented in a listing.

8.4.3.2. Prior/Subsequent Anti-Cancer Procedures

The prior/subsequent anti-cancer procedures will be provided in listings.

8.4.3.3. Subsequent Systemic Anti-Cancer Therapies for AML

The number and percentage of subjects with any subsequent systemic anti-cancer therapies (e.g. chemotherapy, immunotherapy) for AML will be presented by dose cohort (Phase 1b) or treatment arm (Phase 2). Summaries will include number of subjects receiving any prior/subsequent systemic anti-cancer therapy for AML, type of therapy received, intent of therapy, and disease status. A subject may have multiple lines and regimens of systemic anti-cancer treatment for AML. A subject which has multiple intents, types and outcomes will be counted multiple times per category. For subjects with systemic anti-cancer therapies, detailed information will be presented in a listing.

8.4.3.4. Subsequent Stem Cell Transplants for AML

The number and percentage of subjects with any follow-up stem cell transplants for AML will be presented by dose cohort (Phase 1b) or treatment arm (Phase 2). For subjects with stem cell transplants, type and disease status at the time of HSCT will be summarized in tables and the detailed information will be presented in a listing.

8.4.3.5. Prior/Subsequent Systemic Anti-Cancer Therapies Other than AML

The number and percentage of subjects with any subsequent systemic anti-cancer medications for diseases other than AML will be summarized in frequency tabulations by ATC third level and PT, and by dose cohort (Phase 1b) or treatment arm (Phase 2). The type of diseases other than AML will be summarized in separate tables. The detailed information will be presented in a listing.

8.5. Prior/On-treatment/Follow-up Transfusions

Prior transfusions are defined as any type of transfusions received in 8 weeks (56 days) prior to the first dose date. On-treatment transfusions are defined as transfusions that are started on or after the start of study drug but before the last dose date + 28 days. Follow-up transfusions are defined as transfusions that are started on or after the last dose date + 28 days.

Subjects who received prior transfusions are considered transfusion dependent at baseline. The number of subjects receiving any transfusion product, and the number of subjects receiving any transfusion of particular type (RBCs, whole blood, platelets, plasma, other) will be summarized by dose cohort (Phase 1b) or treatment arm (Phase 2). On-treatment transfusions and follow-up transfusions will be summarized separately in tables.

In Phase 2, subjects who achieved post-baseline 56-day RBC transfusion independence, i.e., without RBC transfusion for at least 56 consecutive days post baseline during treatment exposure period, will be summarized by baseline RBC transfusion dependence status (Yes vs. No), within each category of best response (e.g., CR, CRi/CRp, PR/MLFS, SD, PD, etc.) and overall.

The post-baseline 56-day Platelet transfusion independence will be analyzed similarly.

For parameters RBC and Platelet in Phase 2, the number of subjects who are transfusion dependent at baseline, the changes from dependence to post baseline transfusion independence during treatment period will be summarized by treatment arm. The time to transfusion independence and duration of transfusion independence will be summarized by treatment arm as well. In addition, duration of transfusion independence will be summarized by with/without transfusion at baseline. For subjects which have multiple transfusion independent periods, time to the first transfusion independence period and duration of longest transfusion independence period will be summarized.

Transfusion type, number of units, reasons for taking transfusion, and dates of transfusions will be listed in a listing.

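### SAP 8.5 defines baseline transfusion dependence by any product but reports conversion to independence separately for RBC and platelets, so subjects given none of that product before first dose can count as converted

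*SAP*

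**What the plan says.** SAP Section 8.5 builds baseline dependence in two steps. First: "Prior transfusions are defined as any type of transfusions received in 8 weeks (56 days) prior to the first dose date". Then: "Subjects who received prior transfusions are considered transfusion dependent at baseline". The section lists the product types as RBCs, whole blood, platelets, plasma and other. Neither document contains another rule for baseline dependence.

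Independence after baseline is defined by product. For RBC it means "without RBC transfusion for at least 56 consecutive days post baseline during treatment exposure period". For platelets: "The post-baseline 56-day Platelet transfusion independence will be analyzed similarly".

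The tables that combine the two are also organised by product:

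- RBC independence "will be summarized by baseline RBC transfusion dependence status (Yes vs. No").
- The conversion analysis opens with "For parameters RBC and Platelet in Phase 2, the number of subjects who are transfusion dependent at baseline" and continues: "the changes from dependence to post baseline transfusion independence during treatment period will be summarized by treatment arm".
- Duration of independence is split by whether the subject had a transfusion at baseline, with no product named.

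**The concern.** A conversion rate is readable only if its denominator consists of subjects who were receiving the product that they are later said to have stopped needing. Here the written baseline rule ignores product and the written outcome rule depends on it. If the two are joined as they stand, the denominator for each product includes subjects who received none of it in the 56 days before first dose. Such a subject meets the independence criterion by continuing as before, and is reported as a change from dependence to independence.

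At stake is whether the RBC and platelet conversion rates mean what their titles say, and whether two programmers working from the same text would produce the same table. Time to independence is exposed in the same way if it is computed in the same subset, because a subject not using the product can begin a qualifying period at once.

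**Working it through.** The SAP states no figure for this analysis, so there is nothing to reproduce beyond 8 weeks = 56 days, which is correct. The check is first of logic, then of size.

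**Classification.** Baseline status in each analysis, under the written any-product rule and under a same-product rule:

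| Received in the 56 days before first dose | RBC analysis: written / same-product | Platelet analysis: written / same-product |
|---|---|---|
| RBC only | dependent / dependent | dependent / **not dependent** |
| Platelets only | dependent / **not dependent** | dependent / dependent |
| RBC and platelets | dependent / dependent | dependent / dependent |
| Plasma only | dependent / **not dependent** | dependent / **not dependent** |
| None | not dependent / not dependent | not dependent / not dependent |

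The bold cells are subjects whom the written rule admits to the denominator and who can then be counted as converted.

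**Size, platelets.** The documents give no transfusion rates, so every input except the arm size is an assumption. Take 66 subjects (the planned combination arm, SAP Section 4.4): 40 with prior RBC, 25 with prior platelets, 20 with both.

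- Platelet recipients: n = 25.
- RBC-only subjects: m = 40 − 20 = 20.
- Dependent under the written rule: n + m = 45.
- Conversion among true platelet recipients: p = 40%, so 10/25.
- Share of RBC-only subjects with 56 platelet-free days on treatment: s.

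Rate under the written rule = (p·n + s·m)/(n + m):

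- s = 60%: (10 + 12)/45 = 49%
- s = 80%: (10 + 16)/45 = 58%
- s = 100%: (10 + 20)/45 = 67%

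**Other mixes.** Two alternatives were tried: 45 RBC, 35 platelets, 33 both (12 RBC-only, 47 in total), and 40 RBC, 15 platelets, 12 both (28 RBC-only, 43 in total). With p from 30% to 50% and s from 60% to 100%:

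- lowest: (0.30×35 + 0.60×12)/47 = 17.7/47 = 38%, against a same-product 30%
- highest: (0.50×15 + 1.00×28)/43 = 35.5/43 = 83%, against a same-product 50%
- holding p at 40%: from (14 + 7.2)/47 = 45% to (6 + 28)/43 = 79%

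**Size, RBC.** Assume 60% of subjects are RBC recipients with 40% converting, and 10% received only other products, of whom 75% stay RBC-free: (0.60×0.40 + 0.10×0.75)/0.70 = 0.315/0.70 = 45%, against 40%. On these assumptions the RBC table moves less, because fewer subjects enter without having had the product.

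**Direction.** The excess is (s − p)·m/(n + m). It is positive only if s exceeds p. If mix and s are the same in both arms, a true between-arm difference is multiplied by n/(n + m), here 25/45 = 0.56, so it shrinks. If mix or s differs between arms, it can move either way.

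**The case against.** The strongest reply is that the section already means a product-specific status. RBC independence is split by a status labelled RBC, platelets are to be handled in the same manner, and the conversion sentence opens by naming the two parameters, which reads naturally as one count of dependent subjects per product. On that reading nothing is miscounted and only a definition is missing.

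Much of this stands. The text does not say that the conversion tables use the any-product status, so a miscount is conditional on a literal reading. But a label is not a derivation rule: the only operative rule says any type, the split for duration of independence names no product, and the place of whole blood is unresolved even on the charitable reading. SAP Section 2 gives pre-specification as the plan's purpose, and this denominator is not pre-specified.

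The analysis is also modest in weight. It sits in SAP Section 8 with no test, confidence interval or decision rule, and is absent from the endpoint lists in Protocol Section 2 (Table 2) and SAP Section 4.2. Hematologic improvement, which is a listed secondary endpoint, has its own lineage-specific criteria (Protocol Appendix G, SAP Section 17.5). That stands in full.

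Finally, subjects who did not receive a product before baseline need not stay free of it. Both arms receive azacitidine, which Protocol Section 7.2.2.3.4 associates with anemia and thrombocytopenia, particularly in the first 2 cycles. That also stands, and is why s is shown as a range.

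**Conclusion.** SAP Section 8.5 conflicts with itself: one written, product-blind rule for baseline dependence, and product-specific tables that need a status it never defines. Taken literally, the rule lets subjects with none of the product in the 56 days before first dose enter the denominator and count as converted, which can inflate the descriptive Phase 2 rates. In the main illustration 40% becomes 49% to 67%; the true size is unknown, and inflation requires that these subjects reach 56 product-free days more often than true recipients convert.

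Three stronger readings are tempting and unsupported. A reader might infer that the tables will certainly be wrong; the product-specific labels leave open that the intended derivation is correct. A reader might say that the extra subjects never needed the product; the data show only that they received none in the 56-day window. And a reader might conclude that the comparison is biased towards the combination arm; the same rule applies to both arms, and with equal mixes the difference is diluted. No primary or listed secondary endpoint is affected.

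**What to change.** Add to SAP Section 8.5 that a subject is RBC dependent at baseline if at least 1 RBC transfusion was given in the 56 days before first dose, and platelet dependent if at least 1 platelet transfusion was given in the same window. Use only the matching product status as the denominator of each conversion table and as the grouping in each table by baseline status, including duration of independence.

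Class whole blood the same way in the baseline-dependence and post-baseline-independence definitions. If it counted as RBC at baseline only, a subject still receiving whole blood could be dependent at baseline and RBC independent on treatment.

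The cost is one SAP sentence. Protocol Section 6.1 already collects type, units, reason and date for the 8 weeks before treatment, and SAP Section 8.2.1 already tabulates baseline units by product, so no new data are needed. The downside is that the reported conversion rates may be lower. If a product-specific derivation is already intended, the only result it could still change is through the classing of whole blood.

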9. STUDY TREATMENTS AND EXTENT OF EXPOSURE

All analyses of treatment exposure will be conducted using the safety population, separately for Phase 1b and Phase 2. Exposure to AG-120, AG-221, and AZA will be included in the treatment exposure summaries. Duration of treatment and number of cycles will be calculated for all treatment arm.

Descriptive statistics for duration of treatment exposure, duration of treatment, average prescribed daily dose, average calculated daily dose, average daily dose, cumulative dose, dose intensity and relative dose intensity, will be presented by dose cohort groups (Phase 1b) and by treatment arm (Phase 2). Individual subject listings will be provided to support the tables.

9.1. Duration of Treatment Exposure and Duration of Treatment

Duration of treatment exposure and duration of treatment will be summarized by study drug compound(s) in each dose cohort (Phase 1b) or treatment arm (Phase 2) (e.g. for Phase 1b, dose cohort AG-120 500 mg +AZA, the data will be presented by AG-120, AZA and AG120+AZA).

Duration of treatment exposure (months) is defined as: $(\text{treatment end date} - \text{treatment start date} + 28 \text{ days}) / 30.4$. The treatment start date is the date of the first dose of study drug, and the treatment end date is the last dose date. If death date or clinical data cut-off date is after treatment end date and earlier than 28 days after treatment end date, duration of treatment exposure is defined as: $(\text{the earlier of death date and data cut-off} - \text{treatment start date} + 1) / 30.4$.

Duration of treatment (months) is defined as: $(\text{treatment end date} - \text{treatment start date} + 1) / 30.4$. The treatment start date is the date of the first dose of study drug, and the treatment end date is the last dose date of study drug. For subjects who are still on treatment at a data cut-off date, treatment end date will be the earlier of data cut-off date and last day that the subjects take study drug collected in eCRF.

See Section 5.1 for cycle length and cycle number calculations. Average cycle length (days), and number of treatment cycles will be summarized by study drug compound(s) in each dose cohort groups (Phase 1b) or treatment arm (Phase 2). For average cycle length, a single average value will be computed for each subject first and then the descriptive statistics will be computed for each dose cohort groups (Phase 1b) and treatment arm (Phase 2). Additionally, the count and percent of subjects by number of cycles of treatment will be provided for each dose cohort groups (Phase 1b) and treatment arm (Phase 2).

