### Study Treatments

AG-120 and AG-221 are administered orally once a day (QD) on Days 1-28 of each 28-day cycle. Subjects should be instructed to take their daily dose at approximately the same time each day  $\pm$  6 hours. Each dose should be taken with a glass of water and consumed over as short a time as possible. Subjects should be instructed to swallow tablets whole and to not chew the tablets. Fasting is required for 2 hours prior to and 1 hour following AG-221 administration. Water is allowed during fasting. Fasting is not required for AG-120 administration.

Azacitidine will be administered SC for 7 days of each 28-day treatment cycle starting on Day 1 during both Phase 1b and Phase 2. Subjects with newly diagnosed AML who are currently receiving their 1st cycle of azacitidine can be screened for the study. On study, Cycle 1 must be started at 28 days after initiation of the pre-study azacitidine.

During the Phase 2 stage, subjects randomized to the azacitidine alone arms will receive azacitidine 75 mg/m^2/day SC for 7 days of each 28-day cycle. All randomized subjects will receive azacitidine 75 mg/m^2/day SC for 7 days every 28 days until the end of the study, unless they are discontinued from the treatment. In addition, subjects may receive best supportive care as needed (please refer to local prescribing information and local therapeutic guidelines for more details on available formulations, preparation, storage conditions [eg, refrigeration], the approved indications, known precautions, warnings, and adverse reactions of best supportive care; (see current version of Prescribing Information), including antibiotics and transfusions, per investigator discretion. In the event that 2 or fewer doses are missed during the 7-day dosing period, dosing should continue so the subject receives the full 7 days of therapy. If 3 or more days are missed during the 7-day dosing period, the investigator should contact the sponsor and a decision on dosing will be made on a case-by-case basis.

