11.1. Adverse Events

Adverse events (AEs) will be analyzed in terms of treatment-emergent adverse events (TEAEs) which are defined as any AEs that begin on or after the start of study drug through 28 days after the last study treatment. All AEs will be coded using the Medical Dictionary for Regulatory Affairs® (MedDRA) Version 22.0. The severity will be graded by the study personnel based on National Cancer Institute (NCI) Common Terminology Criteria for Adverse Events (CTCAE) Version 4.03.

A treatment-related TEAE is defined as TEAE that is assessed by the Investigator to be possibly related to AG120/AG221 or AZA.

[figure not shown]
If a subject experiences the same AE more than once with different toxicity grade, then the event with the highest grade will be tabulated in “by grade” tables. If a subject experiences multiple AEs under the same PT (SOC), then the subject will be counted only once for that PT (SOC).

[figure not shown]
The number of subjects with at least one TEAE will be summarized. The incidence of TEAEs will be summarized by MedDRA SOC and PT. Tables summarizing the incidence of TEAEs will be generated for each of the following:

- Summary of TEAEs
- All TEAEs;
- TEAEs Exposure Adjusted Incidence Rate (EAIR), only for Phase 2;
- TEAEs by Cycle, only for Phase 2;
- TEAE by decreasing frequency of PT;
- TEAEs related to study drug;
- TEAEs by maximum severity;
- TEAEs with CTCAE grade 3 or;
- Related TEAEs with CTCAE grade 3 or 4;
- Serious TEAEs;
- Serious TEAEs related to study drug;
- Serious TEAEs EAIR, only for Phase 2;
- Serious TEAE by decreasing frequency of PT, only for Phase 2;

- TEAEs leading to study drug withdrawn;
- TEAEs related to study drug and leading to study drug withdraw;
- TEAEs with leading to dose reduction;
- TEAEs related to study drug and leading to study drug dose reduction;
- TEAEs leading to study drug dose interruption;
- TEAEs related to study drug and leading to study drug dose interruption;
- All TEAEs resulting in death;
- Related TEAEs resulting in death;
- TEAEs leading to death EAIR, only for Phase 2;
- TEAEs for the following baseline subgroups (provided when the number of subjects are sufficient), only for Phase 2:
 - Gender (male and female);
 - Age (< 65 years, ≥ 65);
 - Baseline ECOG performance status (Grade 0, 1, 2);
 - Baseline ANC value ($\leq 0.5 \times 10^9/L$, $0.5 < 1 \times 10^9/L$, $\geq 1 \times 10^9/L$)
 - Baseline creatinine clearance value (<45, 45-<60, ≥60 mL/min);

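### SAP 9.1 does not truncate treatment exposure when death or data cut-off falls on the last-dose date, so such a subject is credited 27 days beyond the last observable day

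*SAP*

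**What the plan says.** SAP 9.1 defines duration of treatment exposure by default as treatment end minus treatment start plus 28 days, divided by 30.4 to give months. In that paragraph "the treatment end date is the last dose date".

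The exception applies "If death date or clinical data cut-off date is after treatment end date and earlier than 28 days after treatment end date". Exposure then runs to the earlier of death and cut-off, counted inclusively (+1).

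The next paragraph of 9.1, on duration of treatment, says that for subjects still on treatment "treatment end date will be the earlier of data cut-off date and last day that the subjects take study drug collected in eCRF". The end date can therefore equal the cut-off.

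Three other places bear on the consequences:
- Protocol Summary, Study Treatments: "AG-120 and AG-221 are administered orally once a day (QD) on Days 1-28 of each 28-day cycle". Azacitidine is given on 7 days of each 28-day cycle.
- SAP 11.1 lists, among the safety tables, "TEAEs Exposure Adjusted Incidence Rate (EAIR), only for Phase 2", with similar tables for serious events and events leading to death. No denominator is defined.
- SAP 8.5 describes post-baseline transfusion independence as "without RBC transfusion for at least 56 consecutive days post baseline during treatment exposure period", and treats platelets similarly.

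**The concern.** The exception exists to keep exposure from running past the point where a subject can be observed. It fails in the one case where the whole extension is unobservable: treatment end and cut-off (or death) on the same day. The cut-off is then not later than treatment end, the exception is not triggered, and the default formula applies in full. Nothing elsewhere in the SAP repairs this.

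At stake are the exposure summaries in both phases. Depending on definitions the SAP leaves open, the Phase 2 exposure-adjusted adverse event rates and the 56-day transfusion-independence results could also be touched. Extra person-time lowers an adverse event rate. In Phase 2 the extra time would sit mostly in the experimental arm.

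**Working it through.** The plan states no figure that depends on this rule, so there is none to reproduce. The check applies the rule literally.

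**1. The boundary.** Let S = first dose, E = last dose, C = cut-off. Default exposure in days is E − S + 28, which counts through E + 27. The exception applies if E < C < E + 28 and gives C − S + 1. Take 365 days from S to C, counted inclusively:

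| Last dose, days before cut-off | Exception triggered? | Exposure (days) | Days past cut-off |
|---|---|---|---|
| 0 | no | 364 + 28 = 392 | 27 |
| 1 | yes | 365 | 0 |
| 7 | yes | 365 | 0 |
| 27 | yes | 365 | 0 |
| 28 | no (window already over) | 336 + 28 = 364 | none |

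Moving the last dose by one day, from the day before the cut-off to the cut-off itself, moves exposure by 27 days. 27/30.4 = 0.89 month.

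**2. Death on the last-dose date.** Start 20 Aug 2018, last dose and death 1 Jan 2019, cut-off 19 Aug 2019. Literal rule: 134 + 28 = 162 days. Observable: 134 + 1 = 135 days. The excess is again 27.

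**3. Relative size for one affected subject.** 27/180 = 15%; 27/365 = 7.4%; 27/730 = 3.7%.

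**4. Which Phase 2 arm.** Assume every ongoing AG-221 subject has a recorded dose on the cut-off date, and an ongoing azacitidine-alone subject has one with probability 7/28 = 0.25. Let q be the proportion still on treatment with azacitidine alone divided by that with AG-221. The share of affected subjects who are in the AG-221 arm is 66/(66 + 33 × q × 0.25):
- q = 1.5: 66/78.375 = 84%
- q = 1: 66/74.25 = 89%
- q = 0.5: 66/70.125 = 94%
- q = 0: 100%

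With equal retention, about 1 affected subject in 9 is on azacitidine alone.

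**5. Illustration for the arm as a whole.** Assume 11 to 30 of 66 AG-221 subjects are affected and mean exposure is 8 to 12 months. Excess: 11 × 27/30.4 = 9.8 months, or 30 × 27/30.4 = 26.6 months. Base: 66 × 8 = 528, or 66 × 12 = 792 person-months. Extremes: 9.8/792 = 1.2% and 26.6/528 = 5.0%.

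The 11 is the number on AG-221 plus azacitidine on 15 March 2021 (Protocol, Justification for Amendment). That date is not an analysis cut-off, and the count is not split by phase. The 30 and the 8 to 12 months are assumptions only.

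**6. Transfusion independence.** If the window in 8.5 follows the 9.1 dates and unobserved days count as transfusion-free, 29 observed days + 27 unobserved days = 56 would qualify.

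**The case against.** The strongest reply is that this is a boundary slip whose intent is plain from the exception itself, and that its reach is easily overstated. Much of that stands. A reader might infer four stronger things that the documents do not support.

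- *That the error falls almost only on the AG-221 arm.* SAP 9.1 also governs Phase 1b, where AG-120 is taken daily and is equally affected. Within Phase 2 the direction is right, but no on-treatment counts by arm are given for either named cut-off (19 Aug 2019, 19 Aug 2020).
- *That treatment end equals cut-off for most ongoing subjects.* Daily dosing makes this plausible, but the rule uses dosing days recorded in the eCRF. The oral drugs are mostly self-administered, with diary cards brought to visits (Protocol 7.6). If the last recorded dose is even one day before the cut-off, truncation works.
- *That every exposure-adjusted rate is 1-5% too low.* The SAP defines no denominator for these rates. It has two durations in 9.1 and a separate safety treatment period in section 11. If person-time stopped at the first event (an assumption), the effect would differ by event.
- *That transfusion independence is inflated.* SAP 8.5 does not tie its window to the 9.1 formula, which yields a length rather than dates. It sets its own limit for on-treatment transfusions at last dose plus 28 days. Nothing says that days without data count as transfusion-free.

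The outputs concerned are also descriptive: section 11 rules out inferential analysis of safety data. ORR, EFS and OS do not use this rule, and dose intensity (9.3) has its own durations. None of this removes the boundary error, because the rule as written returns a wrong number in a case it expressly allows.

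**Conclusion.** The point holds as a minor error in a stated rule. Exposure is 27 days (0.89 month) too long for any subject whose last recorded dose is on the cut-off date, and for a subject who dies on the day of the last dose with the cut-off 28 or more days later. That size follows from the text alone.

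The number of subjects affected is unknown. The Phase 2 tilt is mainly towards AG-221: 84% to 100% of affected subjects under the retention ratios tried. The 1-5% effect on combination-arm exposure is illustrative and carries over to adverse event rates only if this duration is their denominator. The transfusion effect is conditional in the same way.

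**What to change.** Change the condition in SAP 9.1 to *on or after* the treatment end date, after capping treatment end at the cut-off as 9.1 already does for duration of treatment. Last doses one or more days before the cut-off are then unchanged; the examples above become 365 instead of 392 days and 135 instead of 162.

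A sturdier alternative is to define one exposure end date for everyone: the earliest of the end of the post-dose window, death and data cut-off. Exposure is then (exposure end − start + 1)/30.4. To match the present default, the window ends at last dose + 27 days, because E − S + 28 = (E + 27) − S + 1.

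State in 8.5 that the transfusion-independence window ends no later than that date, and name the denominator of the exposure-adjusted rates in 11.1.

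The cost is a few lines of SAP text and one derivation. Reported exposure becomes slightly shorter for affected subjects; any rate that uses it becomes slightly higher.
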